## **Scientific basis**

Focal epilepsy refers to having seizures arising from a specific part of the brain. In these patients, workup in magnetic resonance imaging is often necessary as patients with structural lesions have a much higher rate of seizures, ranging from 10% to 26% at 1 year and from 29% to 48% at 5 years. However, there is also a subgroup of patients who has epilepsy not adequately controlled by anti-epileptics with unrevealing first MRI study, a dedicated MRI protocol may reveal positive lesion in 30-65% of the cases. In these patients, several tricks can be applied to increase the detection rate. First, the used of a high-resolution MRI on a high-field scanner could be helpful, which can be increased the sensitivity up to 90%. The use of 7T-MRI in further picking up subtle lesions in patients presenting with epilepsy has been investigated, further affirming the role of high resolution MRI imaging. Secondly, the use of dedicated sequences, such as T1-weighted inversion recovery sequences which allow better distinction of grey and white matter, could also reveal subtle lesions such as polymicrogyria or Type 1 focal cortical dysplasia.

Our study is therefore aimed to apply the findings to the local settings, and specifically to investigate if T1-weighted inversion recovery sequences provides additional benefit in picking up more subtle lesions in patients who had an initial first negative MRI.

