## **Study protocol**

This study will be a prospective cohort model comparing baseline MRI and high-resolution MRI in delineation of focal abnormalities accounting for epilepsy.

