### **Patient recruitment**

**Inclusion:** Consecutive patients with drug-resistant focal epilepsy fulfilling the following criteria –

1. Diagnosis of focal epilepsy with a probable site identified, as defined by concordant results from any TWO of the following:
  - Clinical seminology compatible with focal epilepsy.
  - Electroencephalopathy pointing towards a specific site for focal epilepsy.
  - Positive ictal brain scintigraphy with SPECT-CT correlation.

AND

2. Previous MRI (at least one study with protocol tailored for epilepsy) which did not reveal accountable focal lesion.

AND

3. Able to consent for MRI examination (if patient under age of 18, consent for MRI will be obtained from guardian). Patients will be provided information leaflets to read on, and written consent before taking part in this study and MRI examination.

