### **Sample size calculation**

There is no previous studies available specifically on the use of inversion recovery sequences.

Based on previous paper by deSantis et al. with use of 7T MRI the pickup rate of MRI on patients with previous negative MRI would be around 30%. We prudently estimate that as the current MRI, the pick up rate would be lower than an even-higher resolution 7T MRI and approximately at half of previous study quoted (i.e. 15%), and a 5% false negative rate on patients who actually had lesions on previous baseline MRI. With a 80% statistical power and two-tail alpha = 0.05, approximately 22 patients who needs to have both MRI done and undergone surgery. And assuming that only 1/3 of patients who had workup will undergo surgery, approximately 66 patients are required.

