### **MRI scanning**

Patient will be scheduled to be scanned at the Siemens Prisma 3T MRI scanner at MRI facility, the Chinese University of Hong Kong. The scanning protocol consists of the following staple sequences for evaluation of focal epilepsy:

- Axial, Coronal and Sagittal (left and Right) 2D T1-weighted inversion recovery sequences focusing on site of lesion.
- 3D FLAIR T2-weighted MRI whole brain with multi-planar reconstruction (MPR).
- 3D T1-weighted Sagittal MPRAGE (Magnetization Prepared - RApid Gradient Echo) with MPR.

The following sequences will be applied optionally depending on the site of clinical suspicion and whether dedicated mapping will be required:

- Diffuse tensor imaging of whole brain (DTI)
- Functional MRI (fMRI) for mapping of specific cortical function close to the suspected site of lesion.
- Oblique coronal T2-weighted sequences of the hippocampus if suspected hippocampal sclerosis.
- Thin-cut dedicated T2-weighted or proton-density weighted images.

Contrast injection is usually not required unless otherwise clinically needed (e.g. for scanning of additional clinical indications).

The basic sequences will take approximately 30minutes, and the optional sequences (if needed) would be variable, the whole protocol will be completed within 1 hour.

All high-resolution MRIs performed under this study will be reported by board-certified radiologist and be available on patient's electronic health records (ePR).

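### The specific aim is the added value of T1 inversion recovery, but only whole examinations are scored and compared, so no gain can be credited to that sequence

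*Protocol*

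**What the plan says.** The Scientific basis section states two aims. The first is broad: "Our study is therefore aimed to apply the findings to the local settings". The second is narrow: "specifically to investigate if T1-weighted inversion recovery sequences provides additional benefit in picking up more subtle lesions", in patients whose first MRI was negative.

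The sections that follow work at the level of the whole examination:

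- **Study protocol:** the design is a prospective cohort "comparing baseline MRI and high-resolution MRI in delineation of focal abnormalities accounting for epilepsy".
- **Patient recruitment:** the baseline condition is "Previous MRI (at least one study with protocol tailored for epilepsy) which did not reveal accountable focal lesion". Neither the field strength nor the sequences of that scan are fixed.
- **MRI scanning:** the study scan is done at 3T. Its standard set is 2D T1 IR in three planes, whole-brain 3D FLAIR and 3D MPRAGE. DTI, fMRI, oblique coronal hippocampal T2 and thin-cut T2 or proton-density images may be added, depending on the patient.
- **Image interpretation:** localisation is scored on a five-point scale, and a score of 3 or more makes the imaging study positive. No score per sequence is set, and no read with and without IR.
- **Statistical analysis protocol:** the primary outcome is sensitivity and specificity of the two tiers of MRI, compared by chi-square test. The secondary outcomes are defined on the same two tiers.
- **Sample size calculation:** it opens with "There is no previous studies available specifically on the use of inversion recovery sequences" and then plans on a 15% pick-up rate for the study MRI as a whole.

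**The concern.** The protocol treats high resolution on a high-field scanner and dedicated sequences such as IR as two separate ways to raise detection. The study can change both at once, yet it records a single result. IR may also have been part of the earlier epilepsy-tailored scan, because nothing excludes this. The contrast between baseline and study MRI is therefore not a contrast between no IR and IR.

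Followed as written, the plan would leave the question it calls specific unanswered. The practical risk is that a gain of the whole protocol is reported as a benefit of IR and used to justify adding that sequence elsewhere.

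The timing matters too. Once a reader has seen all sequences together, an uninfluenced IR-free score from that reader is lost, and a later analysis plan cannot recover it.

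**Working it through.** The main point needs no arithmetic. What can differ between the two examinations compared:

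| Possible source of a gain | Baseline MRI | Study MRI | Separated by the plan? |
|---|---|---|---|
| T1 IR | open; may be present | always | no |
| 3D FLAIR, 3D MPRAGE | open | always | no |
| Hippocampal T2, thin-cut T2 or proton-density, DTI, fMRI | open | in some patients | no |
| Field strength | open | 3T | no |
| Repeat scan | earlier scan | later scan | no |

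Only one score per reader and examination is set, so no planned comparison isolates the first row.

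The arithmetic shows how much a read with and without IR could yield.

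**Inputs from the Sample size calculation.** Pick-up 15%; 22 patients with both MRIs and surgery; one third operated, so 22 / (1/3) = 66 scanned, which reproduces. The 22 itself does not follow from the stated 15%, 5%, 80% power and two-sided 0.05: two independent proportions give 141 per group. That is a separate matter, and I take 22 and 66 as planned.

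**Assumptions.** The share s of positive study scans seen only with IR is not in the protocol, so I show 25%, 50% and 100%. No finding is lost when IR is opened. The 15% applies equally to operated and to all scanned patients.

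**Expected positive study MRIs.** 22 × 0.15 = 3.3; 66 × 0.15 = 9.9.

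**Discordant pairs needed.** With k discordant pairs all in one direction, the exact two-sided McNemar p-value is 2 × 0.5^k. For k = 5 this is 0.0625; for k = 6 it is 0.031. At least 6 are needed for p < 0.05.

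**Expected IR-only cases and chance of at least 6.** Expected number = n × 0.15 × s. Chance = P(X ≥ 6) with X binomial(n, 0.15 × s).

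| s | 0.15 × s | Expected in 22 | Chance of ≥ 6 in 22 | Expected in 66 | Chance of ≥ 6 in 66 |
|---|---|---|---|---|---|
| 25% | 0.0375 | 0.8 | 0.01% | 2.5 | 4% |
| 50% | 0.075 | 1.7 | 0.5% | 5.0 | 37% |
| 100% | 0.15 | 3.3 | 10% | 9.9 | 94% |

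**Precision of an estimate (Clopper-Pearson, 95%).** Five IR-only cases in 66 is 5/66 = 7.6%, interval 2.5% to 16.8%. With none in 66, the upper limit is 1 − 0.025^(1/66) = 5.4%.

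**Sensitivity to the pick-up rate.** The Scientific basis section cites 30–65% for a dedicated protocol after an unrevealing first scan. In 66 patients, the chance of at least 6 at 30% pick-up is 37% for s = 25% and 94% for s = 50%. At 65% it is 97% and over 99.9%.

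**The case against.** The best case for the plan is that the IR sentence belongs to the background. The operative sections are consistent with each other, they concern baseline against high-resolution MRI throughout, and they serve the broader local-settings aim. The analysis section never calls its outcome an IR effect. No primary estimate or error rate is wrong, and rewording one sentence would remove the conflict. An analysis plan or reading manual not at hand might also record the sequence on which a lesion was seen.

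Much of this is fair. The whole-protocol contrast is valid, and rewording is an acceptable repair. But the protocol itself calls the IR question specific, and its sample size section returns to IR. A note of the sequence on which a lesion was visible would be useful description. It would not show whether the same reader would have called the scan positive without IR.

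A second objection concerns the figures: at pick-up rates above 15%, a test in 66 patients could be well powered. That is correct, as the last step of the working shows. It does not change the defect, which depends on no figure. With the IR-only share unknown, the chance at the protocol's own planning rate runs from 4% to 94%, so a test should not be promised. In the 22 verified cases it is at most 10% at that rate.

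**Conclusion.** The concern holds. The stated specific aim and the planned comparison do not match, and no read or comparison in this protocol isolates IR. A gain of study MRI over baseline MRI can be reported only as the effect of the whole high-resolution protocol, including any change of scanner and the repeat scan.

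This should be fixed before image reading begins. It does not invalidate the study, because the whole-examination comparison stands for the broader aim. What is lost as written is the IR classification of roughly 3 expected positive scans in 22 operated patients, or 10 in 66 scanned. Those counts rest on the protocol's 15% applied equally to both groups. The test chances also rest on the assumed IR-only shares and on no finding being lost when IR is opened; any loss would lower them.

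**What to change.** Add a staged read to Image interpretation:

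1. Each of the same two radiologists scores the study MRI (five-point scale and site) with T1 IR hidden.
2. That score is locked.
3. The reader opens T1 IR and scores again.

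Both scores must be given before the reader sees or writes the formal report, since "All high-resolution MRIs performed under this study will be reported by board-certified radiologist" and that report goes on the electronic record.

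In the Statistical analysis protocol, report the paired difference with and without IR, with a 95% confidence interval, for (a) pick-up in all scanned patients and (b) sensitivity and specificity in those with the surgical or intracranial EEG reference. Label it as estimation, not a hypothesis test. Describe baseline against study MRI as the effect of the whole high-resolution protocol.

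**Cost.** One extra score per reader and case, with no extra scan, reader or patient. If the repeat reads for intra-observer agreement are staged as well, they add one more score each; the protocol should say whether they are. Research reading has to be kept ahead of, or apart from, clinical reporting. A fixed order may slightly favour the second score; locking the first limits this but does not remove it. The estimate will be imprecise, above all in the roughly 22 verified cases.

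**Alternative.** If the staged read is not adopted, reword the aim in the Scientific basis section to the whole high-resolution protocol. That costs one sentence and gives up the IR question.

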## **Study protocol**

This study will be a prospective cohort model comparing baseline MRI and high-resolution MRI in delineation of focal abnormalities accounting for epilepsy.

### **Patient recruitment**

**Inclusion:** Consecutive patients with drug-resistant focal epilepsy fulfilling the following criteria –

1. Diagnosis of focal epilepsy with a probable site identified, as defined by concordant results from any TWO of the following:
  - Clinical seminology compatible with focal epilepsy.
  - Electroencephalopathy pointing towards a specific site for focal epilepsy.
  - Positive ictal brain scintigraphy with SPECT-CT correlation.

AND

2. Previous MRI (at least one study with protocol tailored for epilepsy) which did not reveal accountable focal lesion.

AND

3. Able to consent for MRI examination (if patient under age of 18, consent for MRI will be obtained from guardian). Patients will be provided information leaflets to read on, and written consent before taking part in this study and MRI examination.

### **Exclusion:**

- Patients who are contraindicated to magnetic resonance imaging (such as due to underlying MRI incompatible metallic implants)
- Patients who cannot cooperate for MRI scanning.
- Patients show are unable to provide informed consent.

### **Sample size calculation**

There is no previous studies available specifically on the use of inversion recovery sequences.

Based on previous paper by deSantis et al. with use of 7T MRI the pickup rate of MRI on patients with previous negative MRI would be around 30%. We prudently estimate that as the current MRI, the pick up rate would be lower than an even-higher resolution 7T MRI and approximately at half of previous study quoted (i.e. 15%), and a 5% false negative rate on patients who actually had lesions on previous baseline MRI. With a 80% statistical power and two-tail alpha = 0.05, approximately 22 patients who needs to have both MRI done and undergone surgery. And assuming that only 1/3 of patients who had workup will undergo surgery, approximately 66 patients are required.

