#### Image interpretation

The baseline MRI of the patients will be retrospectively reviewed, while the MRI performed in this study will also be reviewed by two different radiologists. Radiologists are not blinded to the clinical history and site of clinical suspicion but are blinded to the subsequent surgical findings and outcomes.

The localization of the site of epilepsy will be pointed out according to a five-point confidence scale (1: very unlikely, 2: unlikely, 3: equivocal/ suspicious, 4: likely, 5: highly likely).

A likelihood score of 3 or above would indicate a positive imaging study.

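### The 5% false negative rate behind the sample size is defined on patients with lesions on the baseline MRI, a group that inclusion 2 leaves empty by original report, and it shares no denominator with the 15%

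*Protocol*

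**What the plan says.** In the protocol's Sample size calculation, the first planning rate comes from a 7T study, in which "the pickup rate of MRI on patients with previous negative MRI would be around 30" per cent. The protocol then sets the rate for its own scanner "approximately at half of previous study quoted (i.e. 15" per cent). The second rate is a "5% false negative rate on patients who actually had lesions on previous baseline MRI". The remaining inputs are "With a 80% statistical power and two-tail alpha = 0.05". The result is about 22 patients with both MRIs and surgery. With one third of worked-up patients expected to reach surgery, this becomes about 66.

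Under Patient recruitment, inclusion 2 requires: "Previous MRI (at least one study with protocol tailored for epilepsy) which did not reveal accountable focal lesion". The Scientific basis section gives the same target population: "patients who had an initial first negative MRI".

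The Image interpretation section adds that "The baseline MRI of the patients will be retrospectively reviewed", and that a confidence score of 3 (equivocal) or higher counts as positive. The primary outcome in the Statistical analysis protocol is sensitivity and specificity of each MRI against surgical findings, compared by contingency table and chi-square test.

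**The concern.** Each patient has both scans, so the required number depends on the two discordant cells: baseline negative with study MRI positive (gain), and baseline positive with study MRI negative (loss). Both must be shares of the same patients. The protocol gives the gain on patients with a negative previous MRI and the loss on patients with a positive one. The recruitment criteria select the first group and not the second.

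At stake is whether the sample size has a basis in the population to be analysed. Small changes in the loss cell move the requirement a great deal. A sponsor who corrected only the formula and kept the 5% would carry forward a rate for patients whom the study, by original report, does not recruit.

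**Working it through.** **1. The plan's own figure.** The last step is right: 22 × 3 = 66. The 22 could not be reproduced from 15% and 5% at two-sided 0.05 and 80% power:

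- Paired McNemar: about 147 to 155 pairs across asymptotic versions, 168 exact.
- Two independent proportions: 141 per group (160 with continuity correction).
- Arcsine: about 133.
- One-sample formulas: 53 or 78.

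Two near-matches exist, and neither uses the inputs as stated. Two proportions at 30% against 0% give 22 per group, with no halving and no 5%. A one-sided test at a 15:5 split needs about 22.5 discordant pairs, which are not patients, and the protocol says two-tailed.

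**2. The populations side by side.**

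| Source in protocol | Patients described |
|---|---|
| 15% (Sample size calculation) | previous MRI negative |
| 5% (Sample size calculation) | lesions on previous baseline MRI |
| Inclusion 2 | previous MRI without accountable lesion |
| Scientific basis | first MRI negative |
| Re-read (Image interpretation) | recruited patients; some scans may become positive, share not given |

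Only the re-read can supply patients to whom the 5% applies. If a share q of the analysed patients is positive on re-read, the loss cell is q × 5%. If the 15% applies to the remaining patients, the gain cell is (1 − q) × 15%. A patient already positive at baseline cannot contribute a gain.

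**3. Illustration.** With gain g, loss l, s = g + l and d = g − l, the McNemar normal approximation is

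n = [1.960·√s + 0.842·√(s − d²)]² / d²

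The protocol gives no q; 0% to 20% is an assumption.

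- q = 0: g = 0.15, l = 0. n = (0.7591 + 0.3005)² / 0.0225 = 49.9, about 50.
- q = 10%: g = 0.90 × 0.15 = 0.135, l = 0.10 × 0.05 = 0.005. n = (0.7334 + 0.2953)² / 0.0169 = 62.6, about 63.
- q = 20%: g = 0.80 × 0.15 = 0.12, l = 0.20 × 0.05 = 0.01. n = (0.7067 + 0.2890)² / 0.0121 = 81.9, about 82.
- 5% loss and 15% gain applied to everyone: n = (0.8765 + 0.3669)² / 0.0100 = 154.6, about 155.

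These are operated patients. At the protocol's one-third surgery fraction they correspond to about 150, 189, 246 and 465 recruited, against 66.

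**4. Power at 22 operated patients.** From the same approximation, power = Φ([d√22 − 1.960√s] / √(s − d²)):

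- g = 0.15, l = 0: Φ((0.7036 − 0.7591)/0.3571) = 44% (10% exact).
- g = 0.12, l = 0.01: Φ((0.5159 − 0.7067)/0.3434) = 29%.
- g = 0.15, l = 0.05: Φ((0.4690 − 0.8765)/0.4359) = 17% (4% exact).

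**The case against.** The strongest reply is that the recruitment criteria do not exclude a lesion that was present on the earlier scan but not reported, or one judged not accountable. Every baseline scan is re-read, equivocal findings count as positive, and the readers know the suspected site. The 5% may be meant for the patients who turn positive in that way. This stands as far as it goes: a reader might infer that such patients are barred altogether, and the documents do not support that. But the sample size section does not mention the re-read or give a share for it, and a 5% rate within that subset is still not 5% of the patients analysed.

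A second reading takes the phrase to mean lesions that were there but missed at baseline. It is less natural, since the same passage sets these patients beside those with a previous negative MRI. It would not rescue the input either: a lesion missed on both scans is a concordant negative pair, not a loss.

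A third reply is that nobody can show the 5% affected the 22, and that a 5% loss applied to everyone is the cautious choice, needing 155 patients rather than 50. Both parts are correct. A reader might infer that the misplaced 5% made the study too small, or mis-sized it threefold. The documents do not support this, because the 22 does not follow from the stated rates by any method tried. The figures of 50 to 155 are illustrations under McNemar, which the protocol does not name, and none of them is the protocol's own figure.

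Finally, the share of all recruited patients would also be the wrong denominator. The 22 are operated patients with both MRIs, and sensitivity concerns only those with a lesion on the surgical standard. This objection stands, and the fix below follows it.

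**Conclusion.** The point holds as a mis-specified planning input. The 5% belongs to a group that is empty by original report and can be filled only through an unquantified re-read, and it does not share a denominator with the 15%. The protocol itself states the rate as a basis for the sample size, so this is not a detail left to a later analysis plan.

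The size of the effect is conditional. With the 15% applied to patients negative on re-read and q between 0% and 20% (assumed; nothing in the documents caps it), about 50 to 82 operated patients are needed. With 5% loss for everyone the figure is about 155. Even with no loss at all, 22 operated patients give about 44% power under the normal approximation, not 80%. The illustration treats all operated patients as the denominator. Restricting it to those with a surgically confirmed lesion would need rates that the protocol does not give. The shortfall against 22 appears under each of these readings, so it cannot be attributed to the 5%.

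**What to change.** In Sample size calculation, replace the two rates with the two expected discordant shares on one denominator:

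- baseline MRI negative on the study re-read and study MRI positive;
- baseline MRI positive on the study re-read and study MRI negative, written as the expected re-read-positive share times the miss rate.

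The denominator should be operated patients with both MRIs and, for sensitivity, those with a lesion on the surgical standard. Reword the sentence so that it agrees with inclusion 2 and refers to the re-read. Name the formula used, then restate the required number, or the power that 22 operated patients give.

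The cost is a few lines of protocol text and a recalculation. Scanning and reading are unaffected. The drawback for the sponsor is that the stated size or power will become less favourable.

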#### Statistical analysis protocol

The primary outcome of the study is the sensitivity and specificity of the baseline MRI (bMRI) and the high-resolution MRI (hrMRI) studies, based on the standard of surgical findings on patients who underwent either intracranial EEG or surgical resection. Each of the sensitivity and specificity of the

two tiers of MRI studies (baseline MRI and high-resolution MRI) will be compared with use of contingency table and chi-square test.

The secondary outcomes would include the following:

- Number of cases with true positive, and false positive findings on bMRI or hrMRI; and descriptive statistics of findings in patients who had MRI but did not undergo surgery.
- Inter-observer and Intra-observer agreement for findings on bMRI or hrMRI by kappa statistics.

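### The stated 80% power with 22 operated patients (66 recruited) does not follow from the 15% and 5% rates given for it

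*Protocol*

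**What the plan says.** All the inputs are in the Protocol, *Sample size calculation*. A cited 7T study is used to say that "the pickup rate of MRI on patients with previous negative MRI would be around 30" percent. This is halved for the present scanner, and a second rate is added: "i.e. 15%), and a 5% false negative rate on patients who actually had lesions on previous baseline MRI". The result follows at once: "With a 80% statistical power and two-tail alpha = 0.05, approximately 22 patients who needs to have both MRI done and undergone surgery". Only then does the operated fraction enter, "assuming that only 1/3 of patients who had workup will undergo surgery", which turns 22 into 66. The section names no test or formula and gives no detection rate among operated patients.

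Three other sections bear on the inputs:

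- *Patient recruitment* makes this an entry condition: "Previous MRI (at least one study with protocol tailored for epilepsy) which did not reveal accountable focal lesion".
- *Image interpretation* has the baseline scans re-read, with the rule that "A likelihood score of 3 or above would indicate a positive imaging study". A baseline scan can therefore become positive on re-reading.
- *Statistical analysis protocol* compares the sensitivity and specificity of the two scans by contingency table and chi-square test, "based on the standard of surgical findings on patients who underwent either intracranial EEG or surgical resection".

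**The concern.** A reader who takes the two printed rates and the printed alpha and power cannot get to 22 by the usual paired calculation, or close to it. The 15% also belongs to patients with a previous negative MRI, whereas 22 counts operated patients. The text does not connect the two groups.

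The 80% is the only justification offered for both 22 and 66. If the stated rates do apply to operated patients, the sensitivity comparison is more likely than not to be non-significant even when the new sequences perform as assumed. That result would be read as a negative finding from an adequately powered study.

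**Working it through.** **Inputs.** Two-sided alpha 0.05 and power 80% (z = 1.960 and 0.8416), gain 15%, loss 5%, 22 operated patients, operated fraction 1/3, all from *Sample size calculation*. A gain is a patient positive on high-resolution MRI (hrMRI) and negative on baseline MRI (bMRI). A loss is the reverse. Each patient has both scans, so the comparison is paired. For sensitivity, the patients counted are those positive on the surgical reference. The calculation takes all 22 to be so and treats the pick-ups as true positives.

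**Formula.** With gain rate p10, loss rate p01, psi = p10 + p01 and d = p10 − p01, McNemar's test needs

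n = [1.960·√psi + 0.8416·√(psi − d²)]² / d².

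**Trying to reproduce 22 from the stated rates.**

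- 15% vs 5%: psi = 0.20, d = 0.10. (0.8765 + 0.3669)² / 0.01 = 1.546 / 0.01 = **154.6**.
- 15% vs 0%: psi = d = 0.15. (0.7591 + 0.3005)² / 0.0225 = 1.1228 / 0.0225 = **49.9**.

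An unpaired chi-square test gives 141 per group at 15% vs 5% and 48 per group at 15% vs 0%. A one-sample test of 15% against 5% gives 53 (normal approximation) or 66 (arcsine). None gives 22. The 66 from the arcsine method is a coincidence, because the protocol attaches the 80% to the 22 operated patients.

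**Where the loss rate lies.** The 5% is worded as conditional on a lesion at baseline. The paired loss rate is then 5% × (share of patients positive at baseline). Entry requires a prior MRI without an accountable lesion, so baseline positives can arise only on re-reading. That share is not given. If it were 15% to 20% (an assumption), losses would be 0.75% to 1% and McNemar would need about 58 to 62 pairs. The low end of the range 50 to 155 is therefore the more plausible, and 22 lies outside the whole range.

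**Power with 22 patients** (full enumeration of outcomes, two-sided 0.05):

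| Gain vs loss | Exact McNemar | Uncorrected McNemar |
|---|---|---|
| 15% vs 0% | 10% | 42% |
| 15% vs 2.5% | 7% | 27% |
| 15% vs 5% | 4% | 17% |

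The first row is easy to verify. With no losses, the exact test needs at least 6 gains (2 × 0.5⁶ = 0.031) and the uncorrected test at least 4 (chi-square = 4 > 3.84). With 22 patients at 15%, these have probability 10% and 42%.

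**What does return 22.**

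- 45% vs 5%: psi = 0.50, d = 0.40. (1.3859 + 0.4907)² / 0.16 = 3.5218 / 0.16 = **22.0**. The 45% would arise if all hrMRI positives among the 66 (15% × 66 = 9.9, about 10) fell among the 22 operated: 10/22 = 45%.
- 32% vs 0% also gives 22.0, 41% vs 3% gives 21.4, and 50% vs 7% gives 21.7.

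**How far the 45% route depends on its assumption** (n = 22, exact / uncorrected):

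| Share of hrMRI positives operated | Gain rate | 0% losses | 5% losses |
|---|---|---|---|
| All | 45% | 97% / 99.8% | 75% / 83% |
| Two-thirds | 30% | 69% / 93% | 38% / 53% |

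**The case against.** The best defence is that 22 is right and only its basis is missing. Patients with a new lesion are those most likely to go to surgery, so a rate well above 15% among operated patients is reasonable. At 45% vs 5% the standard formula returns 22, and 22 × 3 = 66. The uncorrected test, the closest paired relative of the chi-square test the protocol names, then has 83% power. This stands as a possible explanation, and for that reason a reader should not infer that an arithmetic slip has been shown. It does not rescue the text: the protocol states neither the 45% nor the assumption that every positive is operated, and other pairs of rates give 22 equally well.

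A second objection is that 155 overstates the shortfall, because the 5% is conditional on a baseline lesion. This is correct. An unconditional 5% would, on the protocol's wording, require every baseline scan to be positive, which leaves no room for gains. A reader might infer that the trial needs 155 operated patients, or 465 recruited (155 × 3). The documents do not support that. 155 is the upper limit of a range that starts at 50.

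Third, the exact test is not the protocol's choice. That is why both versions are shown. At the stated rates neither reaches 50% power.

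Finally, a reader might infer that power under the 45% route must fall if fewer than 22 operated patients are positive on the surgical reference. That does not follow if the pick-ups are true. With 16 such patients and the same expected counts, the rates become 9.9/16 = 62% and 1.1/16 = 7%, and power is 76% / 84%, about as before.

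**Conclusion.** The stated power is not supported by the stated inputs. With 15% as the gain rate among operated patients, 80% power needs about 50 pairs at no losses and up to about 155 at 5% losses. With 22 patients, power is 10% exact / 42% uncorrected at the favourable end and 4% / 17% at the other. The 80% is therefore either not delivered or rests on an unstated assumption about which patients are operated, and the protocol does not allow one to say which.

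These figures assume a paired comparison, two-sided 0.05, all 22 patients positive on the surgical reference, and pick-ups that are true positives. Not established are that 45% vs 5% was the sponsor's calculation, that it is the only pair giving 22, or that recruitment must rise.

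**What to change.** Keep 66 scanned and about 22 operated, and rewrite the paragraph. Name the paired test, give the gain and loss rates assumed among operated patients, and say that the calculation treats the pick-ups as true positives on the surgical reference, as sensitivity requires. Then take one of two courses.

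(a) If 22 rests on all hrMRI positives being operated, state and justify that. Give the power with 22 patients at 45% vs 5% (75% exact / 83% uncorrected) and at 45% vs 0% (97% / 99.8%). Show the dependence on the assumption: with two-thirds operated, 69% / 93% at no losses and 38% / 53% at 5% losses.

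(b) If no such assumption was made, withdraw the 80%. State what 22 provides at the given rates (10% / 42% at 15% vs 0%, 4% / 17% at 15% vs 5%) and the precision to expect. A 15% pick-up is about 3 of 22 operated patients, with exact 95% confidence interval 3% to 35%, or about 10 of 66 scanned, 7.5% to 26%.

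The cost is one paragraph, with no extra patients, scans or operations. The downside is that the stated power becomes less favourable, or an explicit assumption has to be defended.
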